 - screening echocardiogram left ventricular ejection fraction (LVEF) <55.0% or any other echocardiogram finding suggestive of clinically relevant cardiomyopathy
 - screening abnormal ECG findings such as: significantly abnormal PR [PR interval >200 msec], QRS intervals or QTc >450 msec for male subjects and >470 msec for female subjects (based on the average of the 3 ECGs)
 - evidence of any heart block
 - evidence of right bundle branch block or left bundle branch block
 - history or family history of prolonged QT syndrome (eg, torsade de pointes) or sudden cardiac death
- 13. Any of the following laboratory abnormalities at screening:
 - platelet count $<75 \times 10^3/\mu L$ or $<75 \times 10^9/L$
 - hemoglobin <11 g/dL or <6.83 mmol/L for male subjects, <10 g/dL or

<6.21 mmol/L for female subjects

- absolute neutrophil count $<1.00\times10^{3}/\mu$ L
- ALT and/or AST >10× upper limit of normal (ULN)
- total serum bilirubin >1.5×ULN
- albumin <3.5 g/dL or <35 g/L
- estimated glomerular filtration rate (eGFR) of $<50 \text{ mL/min}/1.73 \text{m}^2$
- hypo-/hyperkalemia (Grade 2 or higher)
- 14. Current or past abuse of alcohol or recreational or narcotic drugs, which in the investigator's opinion would compromise the subject's safety and/or compliance with the study procedures

Note: Urine will be tested at screening to check the current use of amphetamines, benzodiazepines, cannabinoids, opioids and cocaine. Subjects with a positive drug test may only be included after consultation with the sponsor. Documentation of the investigator's assessment with regard to the subject's safety and compliance must be in place prior to the start of treatment.

- 15. Subject is pregnant, planning to become pregnant (during treatment and up to 12 weeks after the EOT), or breast-feeding female subject (including female subject who discontinues breast-feeding), or male subject whose female partner is pregnant or planning to become pregnant (during treatment and up to 12 weeks after the EOT).
- 16. Has received an investigational drug (including investigational vaccines) or used an invasive investigational medical device within 30 days before the planned first dose of study drug.

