6.4. Study Treatment Stopping Rules

The occurrence of any one of the following treatment-emergent events in any ongoing study using ODV at therapeutic doses:

- 2nd degree Mobitz Type 2 or 3rd degree heart block;
- drop in EF by ≥ 10 points with absolute EF < 50%;
- a cardiac event that is serious, severe or life-threatening;

will lead to stop of recruitment and dosing in all subjects in this study if the event(s) is adjudicated by the DRC to be at least possibly related to the study regimen. Such event(s) will be reported to the sponsor medical monitor within 24 hours. Upon this notification, a safety assessment of the event by the DRC will take place within 72 hours and the outcome of the

assessment and its associated action towards the study will be reported to Health Authorities and Ethics Committees in compliance with safety reporting regulations, as applicable.

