9.2.4. Echocardiography

The cardiac monitoring requirements outlined in the protocol are critical and must be followed for all subjects. Repeated transthoracic echocardiography will be performed at study approved facilities to assess various echocardiographic parameters including LVEF at time points as indicated in the TIME AND EVENTS SCHEDULE. The screening assessment will serve as baseline value. Additional echocardiography may be done, if in the opinion of the investigator, this is clinically indicated or if needed as part of the cardiac events management plan (see Section 9.2.8.7).

Echocardiograms will be performed according to a standard protocol as described in the study manual. The same technique of echocardiography must be used for each assessment. A variety of echocardiographic parameters, including LVEF, will be quantitated and compared over time as an assessment of safety by a central reader. These measures aim to reduce variability and enhance the precision of the study results.

Any clinically relevant changes occurring from signing of ICF onwards until the subject's last study visit must be recorded on the Adverse Event Section of the eCRF.

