9.2.8.7. Cardiac Safety Monitoring

Regular cardiac safety monitoring will be done in this study via assessments of AEs, ECGs, and regular echocardiograms.

For all subjects enrolled in this study, LVEF at screening must be $\geq 55.0\%$ (see Section 4.2). Screening echocardiography will not only be used for assessing eligibility but will also be considered as the baseline measurement. Appearance or changes in symptoms or findings in echocardiogram may trigger the following treatment stopping criteria²⁶:

- Asymptomatic patients with no clinical evidence of congestive heart failure:
 - If the absolute decrease from baseline in LVEF is $\geq 10.0\%$ (eg, 59.0% to 49.0%) and resulting in an LVEF of <50.0%, discontinue AL-335, ODV, and SMV.
 - If the absolute decrease from baseline in LVEF is >5.0% and ≤10.0%, or >10.0% and resulting in an LVEF ≥50.0%, an assessment of the subject's clinical status, including symptoms, physical examination, and other clinical parameters should be made before deciding whether to stop or continue study drugs.
- For subjects with symptoms (eg, dyspnea, orthopnea) or signs of congestive heart failure (eg, S3 gallop, pedal edema, pulmonary edema):
 - If the absolute decrease from baseline in LVEF is \geq 5.0%, discontinue AL-335, ODV, and SMV.

For all cases described above, a mandatory assessment and urgent cardiology referral should be initiated. The LVEF decrease must be reported to the medical monitor within 24 hours, so that the clinical case and workup and treatment strategy can be discussed.

The cardiology assessment should include, but is not limited to, the following:

- Review of the cardiopulmonary body systems
- Troponin I assessment
- 12-lead ECG
- Repeat echocardiography (at study approved facility)

Echocardiography must be performed at study approved facility on any subject who develops symptoms or signs of possible congestive heart failure (eg, dyspnea, orthopnea, S3 gallop, pedal edema) during the study, regardless of the timing of such symptoms, including during the Follow-up Period.

For all subjects enrolled in this study, triplicate ECGs will be taken at screening and at regular intervals during the study period. Appearance or changes in symptoms or clinically significant findings in ECG may trigger the following treatment stopping criteria:

- 1. If a 1st degree AV block is diagnosed and

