10.2. Discontinuation of Study Treatment/Withdrawal from the Study

Discontinuation of Study Treatment

A subject will not be automatically withdrawn from the study if he or she has to discontinue treatment before the end of the treatment regimen.

A subject's study treatment must be discontinued if (see Section 9.2.8 for more details):

- The investigator believes that for safety reasons or tolerability reasons (eg, AE) it is in the best interest of the subject to discontinue study treatment
- The subject becomes pregnant
- The subject has a Grade 4 rash; see Section 9.2.8.1
- The subject has a Grade 3 or 4 allergic reaction; see Section 9.2.8.2
- The subject has a confirmed Grade 4 ALT and/or AST value that is >2 times the baseline value; see Section 9.2.8.3
- The subject has a confirmed Grade 4 bilirubin elevation; see Section 9.2.8.3
- The subject has severe worsening of hepatic disease; see Section 9.2.8.4
- The subject has a confirmed diagnosis of pancreatitis; see Section 9.2.8.5
- The subject has clinical signs suggestive of muscle injury; see Section 9.2.8.6
- The subject has evidence of cardiac toxicity, see Section 9.2.8.7
- The subject has evidence of renal toxicity, see Section 9.2.8.8.

- Clinical Protocol 64294178HPC2003 Amendment 5
- The subject has a Grade 4 AE or a Grade 4 laboratory abnormality at least possibly related to 1 of the study drugs; see Section 9.2.8.9

Note: For laboratory abnormalities triggering treatment discontinuation, see the toxicity management plans described in Section 9.2.8.

- The subject requires treatment with any of the medications reported on the list of disallowed medications; see Section 8.
- The subject meets a treatment stopping rule for viral breakthrough (see Section 6.3)
- One of the study treatment stopping rules is met (see Section 6.4).

If a subject prematurely discontinues study treatment for above-mentioned reasons, he or she will proceed with a Treatment Withdrawal Visit and will subsequently enter the Posttreatment Follow-up Period. Additional unscheduled visits may be performed for safety/tolerability reasons, if needed.

Withdrawal From the Study

A subject will be withdrawn from the study for any of the following reasons:

- Lost to follow-up
- Withdrawal of consent
- Death

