The ECG variables that will be analyzed are heart rate, PR interval, QRS interval, RR interval, QT interval, and QTc interval using the following correction methods: QTcF (primary correction method)¹⁰ and QT corrected according to Bazett's formula (QTcB).³

QTc data will be analyzed according to the International Conference on Harmonisation (ICH) E14 Step 4 Guidance (May 2005)¹⁴ (see also Attachment 2).

Descriptive statistics of QTc intervals and changes from baseline will be summarized at each scheduled time point. The percentage of subjects with QTc interval >450 msec, >480 msec, or >500 msec will be summarized, as will the percentage of subjects with QTc interval increases from baseline >30 msec or >60 msec.

All clinically relevant abnormalities in ECG waveform that are changes from the baseline readings will be reported (eg, changes in T-wave morphology or the occurrence of U-waves.

Echocardiography

Echocardiographic data will be summarized by key parameters, including LVEF. Descriptive statistics for the echocardiography parameters will be calculated at baseline and for observed values and changes from baseline at each scheduled time point. Frequency tabulations of the abnormalities will be made.

Descriptive statistics of LVEF and mean change from baseline will be summarized at each scheduled time point. Time of onset for LVEF decrease and duration, the percentage of subjects with a decrease in LVEF >10.0% from baseline, with reversible decrease in LVEF and with no resolution of the decreased LVEF will be summarized.

All clinically significant abnormal findings on echocardiography that are changes from baseline readings will be reported.

Vital Signs

Descriptive statistics of pulse rate, and blood pressure (systolic and diastolic) (supine) values and changes from baseline will be summarized at each scheduled time point. The percentage of subjects with values beyond clinically important limits will be summarized (see Attachment 2).

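### An asymptomatic LVEF fall of exactly 10.0 points to below 50% meets both the mandatory-stop rule and the discretionary rule in Section 9.2.8.7

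*Protocol*

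**What the plan says.** Section 9.2.8.7 gives two bullets for asymptomatic subjects with no clinical evidence of congestive heart failure.

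- The mandatory-stop bullet applies to an absolute fall from baseline of at least 10.0% that ends below 50.0%. It carries its own example and action: "eg, 59.0% to 49.0%) and resulting in an LVEF of <50.0%, discontinue AL-335, ODV, and SMV".
- The assess-then-decide bullet reads "If the absolute decrease from baseline in LVEF is >5.0% and ≤10.0%, or >10.0% and resulting in an LVEF ≥50.0" (percent). In that range the subject's clinical status is assessed first, and stopping or continuing is decided afterwards.

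For both bullets, "For all cases described above, a mandatory assessment and urgent cardiology referral should be initiated", and the fall must reach the medical monitor within 24 hours.

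Other sections bear on the same threshold:

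- Section 6.4 (study-wide stopping) uses "drop in EF by ≥ 10 points with absolute EF < 50" (percent).
- Section 10.2 lists among the reasons for which treatment must be discontinued: "The subject has evidence of cardiac toxicity, see Section 9.2.8.7".
- Section 4.2 excludes a "screening echocardiogram left ventricular ejection fraction (LVEF) <55.0" (percent), and Section 9.2.4 states "The screening assessment will serve as baseline value". Every baseline is therefore 55.0% or higher.
- Section 11.4 will summarise "the percentage of subjects with a decrease in LVEF >10.0% from baseline".

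**The concern.** The two bullets in Section 9.2.8.7 prescribe different actions, so each LVEF fall should belong to only one of them. At a fall of exactly 10.0 points ending below 50%, the first bullet's lower limit and the second bullet's upper limit both include the value. The case that the protocol uses to illustrate a mandatory stop thus also fits the wording of the discretionary rule.

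What is at stake is a cardiac stopping decision for a drug whose target organ of toxicity is the heart (Section 1.3.2.2), in a study whose primary endpoint is safety and names echocardiograms. An investigator who reads only the second bullet could think that continuing is allowed.

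The secondary concern is the reporting threshold in Section 11.4. It gives no unit for the change and uses a strict inequality, whereas the stopping rules in Sections 9.2.8.7 and 6.4 are in absolute points and include the value 10.

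**Working it through.** Let B be baseline LVEF, F the follow-up value and d = B − F in percentage points. From Sections 4.2 and 9.2.4, B ≥ 55.0.

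1. **Rules as written (Section 9.2.8.7, asymptomatic).** Bullet 1 (stop): d ≥ 10.0 and F < 50.0. Bullet 2 (assess, then decide): 5.0 < d ≤ 10.0, or d > 10.0 and F ≥ 50.0.

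2. **The protocol's own example.** 59.0 − 49.0 = 10.0 and F = 49.0 < 50.0, so bullet 1 is met, as the protocol says. Since 5.0 < 10.0 ≤ 10.0, the first limb of bullet 2 is met as well.

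3. **Where the bullets overlap.** Bullet 1 needs F < 50.0, which rules out the second limb of bullet 2. The first limb needs d ≤ 10.0 and bullet 1 needs d ≥ 10.0, so d = 10.0 exactly. Then F = B − 10.0 < 50.0 gives B < 60.0, and eligibility gives B ≥ 55.0.
   - Whole percents: 55→45, 56→46, 57→47, 58→48, 59→49, which is 5 pairs.
   - One decimal: 55.0→45.0 to 59.9→49.9, which is 50 pairs.

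4. **Gaps as written.** Falls with 5.0 < d ≤ 10.0 are in bullet 2. Falls with d > 10.0 are in bullet 2 if F ≥ 50.0 and in bullet 1 if F < 50.0. No fall above 5.0 points is uncovered.

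5. **Could the 50.0% floor belong to both limbs of bullet 2?** That would remove the overlap, but falls with 5.0 < d < 10.0 ending below 50.0% would then fall under neither bullet, for example 55.0→48.0 (d = 7.0). At one decimal, B = 55.0 gives 49 such pairs, B = 55.1 gives 48, and so on down to 1 at B = 59.8. The total is 49 × 50 / 2 = 1,225 uncovered pairs, so this reading is not tenable.

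6. **Corrected bullet 2:** 5.0 < d < 10.0, or d ≥ 10.0 and F ≥ 50.0. Falls with 5.0 < d < 10.0 are in bullet 2 only. Falls with d ≥ 10.0 are in bullet 1 if F < 50.0 and in bullet 2 if F ≥ 50.0. That leaves 0 overlaps and 0 gaps at either resolution.

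7. **Section 11.4 on its two possible readings.**
   - Absolute points: 10.0 > 10.0 is false, so the 59.0→49.0 subject is not counted. The same 5 (or 50) pairs are left out. With ≥ 10.0 points, none is.
   - Relative change: 10.0 / 59.0 = 16.9%. Across the boundary range it runs from 10.0 / 55.0 = 18.2% to 10.0 / 59.9 = 16.7%. All exceed 10.0%, so every boundary case is counted.

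**The case against.** The strongest reply is that the protocol already resolves the overlap. Bullet 1 is mandatory and uses the boundary value as its example. Stopping complies with both bullets, and only continuing breaches one. Section 6.4 includes the boundary, and Section 10.2 sends the reader to Section 9.2.8.7 for treatment that must be discontinued. No investigator handles the case alone either, since urgent cardiology referral with repeat echocardiography, and a report to the medical monitor within 24 hours, apply under both bullets. All of this stands and limits the consequence. It does not make the wording correct: a stopping rule should not depend on other sections to settle its own worked example.

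On Section 11.4, a reader might infer that the summary definitely drops a subject stopped under the rule. The document does not support that. The section states neither absolute nor relative change, and on the relative reading the subject is counted. A descriptive cut-off also need not copy a stopping rule, and the protocol leaves specific details to the SAP. Even on the absolute reading the subject would not disappear from the report. Section 11.4 also promises LVEF changes at each scheduled time point, onset and duration of LVEF decreases, abnormality tabulations, and reporting of clinically significant findings. What stands is that the unit is unstated and that one of the two readings is out of step with the stopping rule.

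A reader might also want a probability that the boundary is hit. The protocol gives neither LVEF variability nor reporting precision. Any figure would also depend on how strongly follow-up LVEF is assumed to track baseline, so none is quoted here.

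**Conclusion.** The contradiction in Section 9.2.8.7 is real, follows from the text alone, and is confined to one value: an asymptomatic fall of exactly 10.0 points from a baseline of 55.0% to 59.9%. The intended action is to stop. The protocol does not in substance make that stop optional, although the second bullet read in isolation might suggest it.

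The practical effect is very small. A case needs a baseline in the lowest five points of the eligible range and a change that lands on one exact value, so a boundary case among about 40 subjects is unlikely. Week 4 is the only scheduled on-treatment echocardiogram before the end-of-treatment visit, which limits the occasions further. Whether readings come in whole percents or to one decimal is not stated. That changes the number of boundary pairs (5 or 50) but not the conclusion.

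The Section 11.4 point is secondary and conditional: the unit should be stated, and the boundary case is left out only if the change is meant as absolute. Overall this sits at the bottom of minor.

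**What to change.** In Section 9.2.8.7, reword the range in the second asymptomatic bullet to: *>5.0% and <10.0%, or ≥10.0% and resulting in an LVEF ≥50.0%*. Every fall above 5 points then belongs to exactly one bullet, and the threshold matches Section 6.4.

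In Section 11.4, define the LVEF category as an *absolute decrease of ≥10.0 percentage points* from baseline. This states the unit and counts the boundary stopping case.

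The cost is two inequality signs in the first section, and one sign plus the unit in the second. No new data, visits or procedures are needed.

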9.2.8.8. Renal Safety Monitoring

Renal safety will be monitored by evaluating urine dipstick, in particular urinary proteins, serum creatinine levels, eGFR, and serum chemistry results. The investigator should closely monitor for disturbances in serum creatinine and eGFR. In case renal complications develop, subjects must be treated as clinically appropriate.

The study drugs may be continued if the renal complication is considered not to be related to the study drugs in the opinion of the investigator.

If the eGFR value is $<30 \text{ mL/min/1.73m}^2$, the value must be confirmed by repeat testing during an unscheduled visit preferably within 1 week after the results become available to the study site. If the eGFR value is confirmed to be $<30 \text{ mL/min/1.73m}^2$, all study drugs must be interrupted and renal function will be followed as clinically appropriate. The possibility of restarting treatment should be discussed with the sponsor on a case-by-case basis.

9.2.8.9. Other Toxicities

Note: For Grade 3 or Grade 4 treatment-emergent laboratory abnormalities, subjects should have a confirmatory measurement performed by the local laboratory. The management scheme below is for confirmed treatment-emergent laboratory abnormalities and AEs not included in the sections above and not for isolated and/or nonconfirmed events.

Grade 1

Subjects who develop a Grade 1 AE or Grade 1 laboratory abnormality may continue the intake of study drugs.

Grade 2

Subjects who develop a Grade 2 AE or Grade 2 laboratory abnormality may continue or may discontinue the intake of study drugs based on the investigator's clinical judgment.

Grade 3

Subjects who develop a Grade 3 AE or Grade 3 laboratory abnormality may continue or may discontinue the intake of study drugs at the investigator's discretion if the Grade 3 AE or laboratory abnormality is judged by the investigator to be either "not related" or of "doubtful relation" to any of the study drugs.

For subjects who develop a Grade 3 AE or Grade 3 laboratory abnormality at least possibly related to any of the study drugs, the sponsor needs to be informed and treatment can only be continued if agreed upon by the sponsor and investigator.

Grade 4

Subjects who develop a Grade 4 AE or Grade 4 laboratory abnormality may continue or may discontinue the intake of study drugs at the investigator's discretion if the Grade 4 AE or laboratory abnormality is judged by the investigator to be either "not related" or of "doubtful relation" to any of the study drugs.

Subjects, who develop a Grade 4 AE or Grade 4 laboratory abnormality at least possibly related to any of the study drugs, should discontinue all study drugs.

9.3. Pharmacokinetics

9.3.1. Evaluations

Venous blood samples of approximately 5 mL will be collected for the measurement of plasma concentrations of AL-335 (and metabolites), ODV, and SMV at the time points specified in the TIME AND EVENTS SCHEDULE and TIME AND EVENTS SCHEDULE: Rich serial PK Assessments. At the Week 12 Follow-up Visit, venous blood samples of approximately 3 mL will be collected for the measurement of plasma concentrations of ODV.

Sparse PK Sampling

All subjects will undergo sparse PK blood sampling at Weeks 2, 4, 6, and at the EOT (Weeks 8) Visit (Cohort 1), or Weeks 2, 4, 6, 8 and at the EOT (Weeks 12) Visit (Cohort 2), predose, between 2- to 4-hours postdose, and between 4- to 6-hours postdose for the measurement of plasma concentrations of AL-335 (and metabolites), ODV, and SMV (see the TIME AND EVENTS SCHEDULE). At the EOT visit, intake of study drugs should take place on site when predose PK sampling is performed. At Week 4, no sparse PK sample will be taken for subjects participating in the rich serial PK substudy. At the Week 12 Follow-up Visit, sparse PK sample (3 mL) will be taken at any time for the measurement of plasma concentrations of ODV.

On the days of sparse PK blood sampling, the exact dates and times of PK blood sampling must be recorded according to the Laboratory Manual. The exact date and time of study drug intake on the day of the PK blood sampling and the previous day need to be recorded in the eCRF. It will be recorded whether the subjects took their study drugs in fed state (during or within 15 minutes after completion of a meal) on the day of PK blood sampling and on the previous day.

Rich Serial PK Sampling for Noncompartmental PK Analysis in the PK Subgroups

In the rich serial PK substudy, rich serial PK blood sampling will be performed in approximately more than 6 subjects in each cohort.

Subjects participating in the rich serial PK substudy will undergo rich serial PK sampling at their Week 4 Visit, at 10 different time points within the dosing interval (see TIME AND EVENTS SCHEDULE: Rich serial PK Assessments). Intake of study drugs should take place on site when predose PK sampling is performed. For the intensive PK samples of the rich PK substudy, noncompartmental PK analysis of AL-335 (and metabolites), ODV, and SMV will be performed using actual sampling time points and plasma concentrations obtained from rich serial PK blood sampling at Week 4.

The first sample should be collected before study drug intake (within 0.5 hour before). Thereafter, study drugs (AL-335, ODV, and SMV) will be administered with a breakfast. Samples 2 to 10 should be collected at 1, 2, 3, 4, 6, 8, 10, 12, and 24 hours after study drug intake. No additional sample is needed to cover the PK sample to be taken at any time during the visit at Week 4. This sampling schedule may require an overnight stay and the 24-hour PK sample must be taken before study drug intake on the morning following the overnight stay.

A breakfast should be eaten completely within 30 minutes. The study drugs should be taken during or no later than 15 minutes after completing the breakfast.

On the days of rich PK blood sampling, the exact dates and times of PK blood sampling must be recorded according to the Laboratory Manual. The exact date and time of study drug intake on the day of the PK blood sampling and the previous day need to be recorded in the eCRF. In addition, start and end times of accompanying meal on the day of the PK sampling need to be

recorded. It will be recorded whether the subjects took their study drugs in fed state (during or within 15 minutes after completion of a meal) on the day prior to the visit.

